### 3. Study Design

As mentioned in section 2, this project consists of two distinct aims: aim 1 (usability) and aim 2 (RCT). Aim 1 of this project will be conducted within a population of 5 to 15 healthy volunteers using a single study visit lasting approximately 30 to 60 minutes in which they will be asked to provide feedback on the app and its contents. Individuals enrolled into this aim will be asked to provide feedback via written communication. Feedback will be used to improve the app for Aim 2 (RCT).

Aim 2, which is the main focus of this exploratory pilot randomized clinical trial (RCT) is to be conducted within a population of 60 cardio-respiratory survivors with a 3-month follow-up. Eligible patients will be those individuals who are admitted to the hospital and receive treatment for cardio or respiratory failure. Additional characteristics of the target population are those that exhibit high psychological distress, as defined by their scoring at the time of hospital discharge via the Hospital Anxiety and Depression Scale (HADS) and Post Traumatic Stress Scale (PTSS) surveys. Eligible patients will be identified via daily electronic medical record (EMR) review and approached for consent while still hospitalized. Patients will be

asked to complete app registration and baseline survey completion post-consent, but at the time of hospitalization, if possible. Upon discharge, patients will be asked to complete survey 1, T1, to assess their levels of psychological distress. Should the patient demonstrate high enough levels of psychological distress, they will be randomized to 1 of 3 treatment arms:

- Arm 1: mCST Intervention Group 1 (self-directed coping skills training app with CST therapist intro call)
- Arm 2: mCST Intervention Group 2 (self-directed coping skills training app only)
- Arm 3: usual care (control group; no CST therapist and no coping skills training app)

Each participant, regardless of randomization arm will be asked to complete the following surveys at the listed time points below:

- Baseline (during hospitalization, post consent)
  - Collect sociodemographic data and establish baseline psychological distress.
- T1 (at the time of hospital discharge, within 1 week of returning to home but no more than 1 month (30 days) from discharge)
  - Complete the HADS, PTSS, and PHQ-10, QOL 100-point visual analog scale, IADL/ADLs
- T2 (1 month (30 days) post date of discharge; up to 2 months (60 days) for completion)

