  - Complete the HADS, PTSS, and PHQ-10, QOL 100-point visual analog scale, IADL/ADLs
- T3 (3 months (90 days) post date of discharge; up to 4 months (120 days) for completion)
  - Complete the HADS, PTSS, and PHQ-10, QOL 100-point visual analog scale, IADL/ADLs, CSQ-8

Additionally, each participant, regardless of randomization arm, will be asked to complete a weekly HADS survey during the first month (30 days) of study participation, post discharge. The purpose of this survey is to assess overall psychological distress.

For those patients who are assigned to arms 1 or 2, they will be asked to utilize the app for 1 month (28 days). During that 1 month time period, they will be provided with weekly coping skills, as listed below:

- *Week 1: Progressive Muscle Relaxation and Pleasant Imagery*
  - Week 1 includes two coping skills: progressive muscle relaxation and pleasant imagery. Progressive muscle relaxation is the practice of taking time to enjoy the *feeling* of relaxation, whereas the practice of pleasant imagery is using one's imagination to create a pleasant or happy scene, like a pleasant daydream, that they can return to at any moment.
- *Week 2: Pleasant Activities and activity-Rest Cycling*
  - Week 2, like week 1, includes two coping skills: pleasant activities and activity rest cycling. Pleasant activities is intended to help one *plan* to do regular activities by 1) convincing one's self to find time and effort to complete the activity/ies they enjoy, 2) develop a schedule to help them commit to completing the activity/ies, and 3) encourage one to hold themselves and have others help hold them accountable to complete the activity/ies. Activity rest cycling is a practice in which one learns to overcome "over activity", meaning doing too much at one time or over doing a particular activity. There are 3 components to practicing activity rest cycling: 1) identify activities that one may over-do, 2) take note of how one feels after the activity is completed, and 3) set time limitations on how long one will perform the activity.
- *Week 3: Fast Relax and Managing Negative Thoughts*

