- **Withdraw by PI or Self:** defined as any individual who voluntarily consents to participate in the study, but is then withdrawn from the study. The PI may withdraw a participant at any time without their consent if the PI deems it is in their best interest to no longer participate OR the patient demonstrates continuous lack of compliance with study protocol and study procedures. Additionally, if the patient is re-admitted to the hospital during the time of randomization, he/she will be withdrawn from the study by the PI. The study team may re-enroll the patient at the time of discharge following the same screening procedures. The patient may withdraw themselves at any time; the study team will be asked to document the reason for withdraw for study records. Patients who reach this status have no additional follow-ups or study requirements. Patients who are assigned this status must be maintained on the enrollment log.
- **Lost to Follow-Up (LTF):** defined as any individual who voluntarily consents to participate in the study but after non-compliance and at least 3 documented, attempted contacts appropriately spaced 1-5 days apart, the individual will be considered LTF.
  - For aim 2 only:
    - Patients who reach this status have no additional follow-ups or study requirements. Patients who are assigned this status must be maintained on the enrollment log.
    - A patient who returns the study team's contacts within 1 week of last attempted contact may resume study participation.
- **Completed:** defined as any individual who both consented and randomized to the study and completed T1-T3 (aim 2 only) or any individual who completed assigned study visit (aim 1 only). Individuals who reach this status have no additional follow-up or study requirements. Individuals who are assigned this status must be maintained on the enrollment log.

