- **T3 (Day 90) (+30 days):** this visit is to occur post 3 months randomization for those patients who remain eligible to participate in the study. HADS, PTSS, and PHQ-10 surveys will be administered again. If the patient's survey scores indicate high levels of distress, as defined by a triggered SI alert or increased distress score from T1, a delegated study team member will contact the patient for safety precautions. At the completion of this survey and assuming no additional follow-up is required due to high levels of distress, the patient's participation in the study is complete.

Additionally, each patient who is randomized will be asked to complete:

- **Weekly Check-In:** for those patients who are eligible for randomization to either Groups 1, 2 or 3, a weekly check-in will be completed by a delegated study team member and/or via the app (randomization group dependent). This weekly check in (i.e., HADS survey) will be available beginning day 4 of the week until day 7 of the week.

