#### Adverse events (AEs), serious adverse events, (SAEs) and unanticipated problems (UPs).

It is recognized that there is a slight risk that some participants may become distressed when completing self-report measures or participating in interviews. When necessary, participants who experience psychological distress *related to completing questionnaires* will be referred for appropriate psychiatric or psychological care. All participants will have access to the PI’s contact information 24 hours a day (shown in the consent form). If a telephone interview is required, a trained study team member who has been trained to be sensitive to the nature of these issues will conduct it.

It is anticipated, in this study, for AEs to be extremely rare as it is a behavioral study. However, it is possible that participants could become distressed in a hospital setting or post-discharge due to increased illness and/or limitations. As such, participants could exhibit signs of and/or experience suicidal ideations or be admitted for mental health symptoms. Therefore, for this study, only increased levels of distress related to completing the questionnaires or completing the coping skills practice and/or suicidal ideations will be considered AEs.

Like, AEs, it is not anticipated that SAEs will occur. However, for this study, an SAE would be defined as a suicide attempt, a hospitalization (post hospitalization that initiated the patient’s eligibility for study

participation), or death. All serious adverse events will be reported within the standard timelines required to the IRB, study sponsor, and/or DSMB, as appropriate and when applicable.

Given the nature of this study, it is anticipated that most enrolled patients will not complete their study visits within the assigned protocol window. Additionally, it is expected that visits and/or mCST practices will be missed. As such, these will not be considered protocol deviations. Should other protocol deviations or unanticipated problems occur, they will be discussed with the PI, documented, and reported to the IRB, study sponsor, and/or DSMB, as appropriate and when applicable.

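### The lost-to-follow-up rule can end a patient's follow-up for good 9–17 days after the first unanswered contact, while the T2 and T3 windows are still open

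*Protocol*

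**What the plan says.** Protocol section 7 (Screening, Recruitment and Consent, status list) assigns lost-to-follow-up status after non-compliance, which it does not define, and "at least 3 documented, attempted contacts appropriately spaced 1-5 days apart". For the randomised trial the consequence is: "Patients who reach this status have no additional follow-ups or study requirements". There is one way back: "A patient who returns the study team's contacts within 1 week of last attempted contact may resume study participation".

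Other parts of the protocol are more lenient:

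- Section 3 schedules "T2 (1 month (30 days) post date of discharge; up to 2 months (60 days) for completion", and T3 at "3 months (90 days) post date of discharge; up to 4 months (120 days) for completion".
- Section 5 (discharge exclusions) excludes a patient for not opening the app only after a full month from randomisation.
- Section 12 (adverse events) states that "it is anticipated that most enrolled patients will not complete their study visits within the assigned protocol window". It also expects missed visits and missed practice sessions, and does not count them as deviations.
- Section 3 says staff may contact a patient who stops using the app for any length of time. Control patients receive surveys only.

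Section 4 makes retention part of the primary feasibility outcome. SAP section 3.1 sets its benchmark at 80% and notes that the feasibility benchmarks still need tighter definition. The Completed status in protocol section 7 requires T1 to T3.

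**The concern.** The definition does not refer to T2 or T3. As written, a missed app task or weekly check-in, followed by a short run of unanswered contacts, can end collection of the trial's outcomes. Patients recovering at home from cardiorespiratory failure may well be silent for two or three weeks, and the protocol itself expects missed visits.

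Two things are at stake. Retention is a result that the pilot is meant to pass on to the definitive trial. If the rule closes out patients who would have answered later, the observed figure partly measures the rule. Secondly, T2 and T3 HADS and PTSS scores are lost for patients who could still have given them. The electronic record is checked for deaths before T2 and T3, so vital status may survive, but the questionnaire scores would not.

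**Working it through.** The documents state no expected loss rate and no dropout allowance, so there is no plan figure to reproduce. The check is a day count, followed by an illustration on assumed rates.

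**1. Time to the status.** Three attempts have 3 − 1 = 2 gaps of 1–5 days each, so 2 × 1 = 2 to 2 × 5 = 10 days from first to third attempt. Adding the 7-day return period gives 9–17 days until the status is final. These are minimums, because three attempts is a floor.

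**2. Against the windows.** Section 3 counts T2 and T3 from discharge: T2 due day 30, closing day 60; T3 due day 90, closing day 120. The earliest scheduled survey after randomisation is the week-1 check-in ("This weekly check in (i.e., HADS survey) will be available beginning day 4 of the week until day 7 of the week"), so it is missed at the end of day 7. Attempts are taken to start the next day. Days below are from discharge.

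| Lapse | First attempt | Status reached | Final | Final to T3 close (day 120) |
|---|---|---|---|---|
| Week-1 check-in, randomised at discharge | 8 | 10–18 | 17–25 | 95–103 |
| Week-1 check-in, randomised day 30 | 38 | 40–48 | 47–55 | 65–73 |
| T2 missed when due | 31 | 33–41 | 40–48 | 72–80 |
| T3 missed when due | 91 | 93–101 | 100–108 | 12–20 |

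If the first attempt in row 1 is made on day 7 itself, the status is final on days 16–24, which leaves 120 − 24 = 96 to 120 − 16 = 104 days. Across the first three rows the range is therefore 65–104 days. Attempts that start later shorten these gaps day for day.

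In row 1 the patient is closed out before T2 is due. In rows 2 and 3 T2 is already due but still open, with 60 − 55 = 5 to 60 − 47 = 13 days left in row 2 and 60 − 48 = 12 to 60 − 40 = 20 in row 3. In row 4, counted from when the status is reached, the gap is 120 − 101 = 19 to 120 − 93 = 27 days. The T3 case is thus about two to four weeks.

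The Study Visits text counts T2 and T3 from randomisation instead. On that clock T3 closes on day 90 + 30 = 120 after randomisation, so row 2 would become 95–103 days, as in row 1.

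**3. Room under the benchmark.** An 80% benchmark allows 0.20 × 60 = 12 losses with the protocol's sample size and 0.20 × 45 = 9 with the SAP's. A few patients who would have answered late can matter.

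**4. Illustration only.** Let *d* be other loss, *L* the share who lapse and meet the rule, and *q* the share of those who would still answer if invited. Retention = (1 − *d*)(1 − *L*(1 − *q*)), and the rule sets *q* = 0. None of these rates is in the documents. Take *d* = 10% and the protocol's 50 app and 10 control patients.

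| Lapse assumed | *q* = 0 (rule) | 25% | 50% | 75% |
|---|---|---|---|---|
| 30% app, 10% control: overall retention | 66% | 72% | 78% | 84% |
| Same: control minus app, points | 18 | 13.5 | 9 | 4.5 |
| 20% in every arm: overall retention | 72% | 76.5% | 81% | 85.5% |
| Same: control minus app, points | 0 | 0 | 0 | 0 |

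For example, under the rule the app arms retain 0.90 × 0.70 = 63%, controls 0.90 × 0.90 = 81%, and overall (50 × 0.63 + 10 × 0.81)/60 = 66%. Retention falls under the rule in every case. A gap between arms appears only if lapse differs between arms.

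**The case against.** **The rule is permissive.** Three attempts is a minimum, non-compliance is undefined, contact after app silence is optional, and missed practices are not deviations. Staff could try for longer and could decide that missed app tasks do not count. This stands, so the finding is about what the rule allows. But nothing requires staff to wait for the survey windows, and two coordinators could apply the text differently.

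**Uneven loss.** A reader might infer that the rule removes more app patients than controls and so biases the comparison. The documents do not support this as a fact. They give no lapse or adherence rates by arm. The weekly HADS check-in, the earliest scheduled survey that can be missed, goes to all three arms under section 3 and Study Visits, although note (d) in Appendix 1 mentions only Arms 1 and 2. If lapse is equal, the gap in loss is zero, and its direction is not certain. What remains is a risk: app silence may prompt contact attempts in Arms 1 and 2, while controls have only surveys to miss.

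**The benchmark.** A reader might also infer that the rule turns a pass on retention into a failure. That depends on the assumed rates: with 20% lapse in every arm, *q* = 25% still misses 80% and *q* = 50% reaches it. The benchmark also has no stated denominator or time point.

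**A pilot with a mixed model.** The trial is not intended to test efficacy, the SAP reports intervals without p-values, and PROC MIXED uses whatever scores exist. This limits the harm to inference, and bias would require loss related to unobserved distress. It does not help retention, which is a primary measure. A patient with only T1 also has no observed change.

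**Limits on contact are reasonable.** People who do not respond should not be pressed. This is a fair constraint on how often to call. It does not require withholding the scheduled T2 and T3 invitations.

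**Conclusion.** The concern holds in a limited form. The rule can close out a patient permanently 9–17 days after the first unanswered contact. For a lapse in month 1 or at T2 this is about 65–104 days before T3 closes, depending on when the patient was randomised and when attempts began. For a lapse that first occurs at T3 it is about two to four weeks. The counts assume the minimum of three attempts, started on the day a survey is missed or the day after.

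The rule does not fit the protocol's own survey windows, its one-month allowance for opening the app, or its expectation of missed visits and practices. Compared with continued invitations, it can only lower retention and the number of T2 and T3 scores; the documents do not let the size be estimated. Differential loss is a plausible risk. Neither a biased comparison between arms nor a changed result against the 80% benchmark is shown.

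**What to change.** - Define non-compliance, and separate missed app tasks and check-ins (adherence) from loss to follow-up (no outcome data obtainable).
- Keep sending T2 and T3 invitations, until each window closes, to every randomised patient who has not died, withdrawn consent, or been withdrawn by the investigator under the protocol's existing rules, including those on readmission and suicidality.
- Assign lost-to-follow-up status only when the T3 window closes without contact, and remove the one-week return limit for completing T2 and T3.
- Reconcile the investigator-withdrawal wording on persistent non-compliance in section 7, so that missed app tasks do not end outcome collection by that route.
- State one clock and one window for T2 and T3, since section 3 and Study Visits differ, and give the retention benchmark a denominator and time point in the SAP.

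The cost is a wording amendment and a little more contact effort, mostly automated invitations. A patient's right to withdraw is unchanged.

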## Study Visits

For aim 1, each participant will be asked to complete a singular study visit that last approximately 30-60 minutes. During this study visit, post consent, the individual will be asked to do the following:

- Find and install the Pattern Health app
- Register to the Blueprint study
- Complete baseline survey
- Randomize to 1 of 3 arms or screen fail purposely
- Provide feedback on app content and usability.

For aim 2, each consented patient will be asked to complete up to four individual study visits.

- **Baseline:** this visit is to occur post-consent (same day, ideally) at the time of hospital admission just prior to discharge. However, this visit may occur at the time of hospital discharge within 1-3 days of returning to home. At this visit, the following will occur:
  - App Registration
  - Baseline Survey Completion
- **T1 (Day 0) (+30 days):** this visit is to occur at the time of hospital discharge to home, ideally within the first week (7 days) of returning to home; however, it can occur up to 1 month (30 days) from the time of hospital discharge to home. At this visit, the patient will complete the T1 survey via the app, which includes the HADS, PTSS, and PHQ-10 surveys. Score dependent, the patient will be randomized to 1 of 3 arms: Group 1 (Blueprint app), Group 2 (Blueprint app + therapist), and Group 3 (control; no Blueprint app and no therapist). If the patient's psychological distress score is too low; he/she will receive an automated alert via the app describing they are not eligible and their study participation is complete.
- **T2 (Day 30) (+60 days):** this visit is to occur post 1 month randomization for those patients who remain eligible to participate in the study. HADS, PTSS, and PHQ-10 surveys will be administered again. If the patient's survey scores indicate high levels of distress, as defined by a triggered SI alert or increased distress score from T1, a delegated study team member will contact the patient for safety precautions.
- **T3 (Day 90) (+30 days):** this visit is to occur post 3 months randomization for those patients who remain eligible to participate in the study. HADS, PTSS, and PHQ-10 surveys will be administered again. If the patient's survey scores indicate high levels of distress, as defined by a triggered SI alert or increased distress score from T1, a delegated study team member will contact the patient for safety precautions. At the completion of this survey and assuming no additional follow-up is required due to high levels of distress, the patient's participation in the study is complete.

Additionally, each patient who is randomized will be asked to complete:

- **Weekly Check-In:** for those patients who are eligible for randomization to either Groups 1, 2 or 3, a weekly check-in will be completed by a delegated study team member and/or via the app (randomization group dependent). This weekly check in (i.e., HADS survey) will be available beginning day 4 of the week until day 7 of the week.

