#### *Specific longitudinal participant oversight plans for severe psychological distress (including suicidal ideation)*

Given the difficult situations faced by patients, we recognize that there is a slight risk that some participants may become distressed completing questionnaires or viewing study materials, as mentioned above.

We will take the following measures to prevent any negative reactions as well as effectively manage any serious distress that occurs:

- (1) All of the in-person and telephone-based data collection sessions will be conducted by study team members who are sensitive to the issues that arise.

(2) Study team members will emphasize to participants that any interviews or other study interactions are participant-controlled. Thus, participants will be instructed that they are in control over what they share and generally how long they discuss any topic that is addressed.

(3) Participants will be told that they can discontinue an interview or telephone session at any time and that they are free to reschedule an interview or treatment session at any time within the week.

(4) Overall, we are very sensitive to the common and pervasive nature of psychological distress among cardiorespiratory failure survivors and are experienced in discussing these issues with them. There is also a potential risk for identifying underlying mental health issues through the mCST sessions, telephone calls, and survey responses. For issues such as passive suicidal ideation or symptoms of depression, anxiety, or PTSD, an informational sheet will be provided with contact numbers for additional mental health services.

Additionally, at the beginning of the program, all subjects will be informed that the training program may uncover unresolved and distressing thoughts or feelings; and a list of resources will be provided at that time.

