### Suicidality Response Plan

Should a patient indicate to a study team member, thoughts of suicidality or ideation of suicidality, the Suicidality Response Plan could be activated.

If the participant is deemed to be at high risk based on direct interaction plus the C-SSRS item response, the delegated study team member will administer the C-SSRS to assess the participant to determine if they endorse active suicidal ideation. The trained staff will also determine if the participant is currently being treated by a mental health professional.

If the patient is deemed not to be actively suicidal, they will be given a list of local mental health resources as follows:

- Duke: Call Emergency Psychiatry at [contact] or [contact], available 24 hours a day, 7 days a week.
- The National Suicide Prevention Lifeline - [name] is a free, 24-hour hotline available to anyone in suicidal crisis or emotional distress.

If the participant is considered actively *suicidal* then at least one of the following plans will be followed depending on the location of the participant for each of the following situations:

- Situation 1
  - If the participant is with one of the study personnel, the study personnel will notify the site PI one of the other PIs immediately.
  - The study personnel will either physically walk the subject to the emergency department, or call a Psychiatric Emergency services number relevant to the site as described above.
- Situation 2
  - If the participant is on the telephone:
    - The study personnel will notify the site PI one of the other PIs immediately
    - The study personnel will stay on the telephone with the subject participant.
    - The study personnel will immediately contact 911 to initiate an on-site rescue if such action is clinically indicated.

- The study personnel will stay on the telephone with the subject until EMS services have contacted the participant.

If the participant is determined to be actively suicidal and require immediate medical therapy, they will be withdrawn from the study.

As described above, all concerns about participant safety will be discussed immediately with the PI - including concerning severe distress that does not involve suicidality.

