#### Period and Frequency for Event Assessment and Follow-Up

Protocol deviations and other unanticipated problems, as well as AEs and SAEs, will be recorded in the data collection system throughout the study and reported, as appropriate, to the IRB, study sponsor, and/or DSMB, when applicable.

The study team will record all reportable events with start dates occurring any time after informed consent is obtained until 7 (for non-serious AEs) or 30 days (for SAEs) after the last day of study participation. At each study visit, the study team will inquire by way of verbal or written request and/or EMR review, of the occurrence of AE/SAEs since the last visit. Events will be followed for outcome information until resolution or stabilization.

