#### Reporting Procedures

##### *Adverse and Serious Adverse Events*

For symptoms that are either great in total burden (i.e., total score is high), a delegated study team member (e.g., therapist) will call the participant to check in. For specific symptoms such as the suicidal ideation, a delegated study team member will also call the participant and assess the severity of the situation, triaging them as appropriate to psychiatric support.

For other matters, the study team will maintain frequent telephone contact with most participants, and can refer those with concerning symptoms.

All deaths will be reported to NHLBI Program Officer and to the DSMB Chair within 72 hours of study's knowledge of death. For each patient who dies, a brief report containing the following variables will be provided:

- Age
- Principal diagnosis
- Number of comorbidities
- Admission APACHE II score
- Days since enrollment
- Brief description of circumstances surrounding death including expected or unexpected.

Serious (fatal or life-threatening) SAEs that are unanticipated and that are related to the intervention will be reported to the NHLBI Program Officer and to the DSMB Chair within 7 days of study staff's knowledge of the SAE.

The summary of all other SAEs will be reported to NHLBI Program Officer and to the DSMB quarterly, unless otherwise requested by the DSMB.

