## Appendix 1: Schedule of Events

	Day 0 (In-Hospital, Baseline)	Day 1 , T1 (Discharge) (+30 days)	Week 1	Week 2	Week 3	Week 4 Day 30, T2 (+60 days)	Day 90 (+30 days), T3
Screening*	X						
Consent (a)*	X						
App Registration*	X						
Baseline Survey (b)*	X						
Usability Survey*							
T1 Survey (c)		X					
T2 Survey (c)						X	
T3 Survey (c)							X
Weekly Check-In (d)			X	X	X		
Progressive Muscle Relaxation and Pleasant Imagery (mCST)			X				
Pleasant Activities and Activity Rest Cycling				X			
Fast Relax and Managing Negative Thoughts						X	
Problem Solving and Maintenance							X
Data Entry (e)	X	X				X	X
AE/SAE assessment (f)	X	X				X	X
Survival Status (f)		X				X	X
End of Study (g)							X

- a) Patients may be approached and consented during their admission, if well enough; their hospitalization (e.g., while in step-down), or within 1-3 days of returning to their home for participation in the study
- b) Completion of the baseline survey includes the patient providing self-reported information such as social and demographic information and general health status.
- c) Surveys 1, 2 and 3 will be completed via the app by all study participants, regardless of arm assignments. Patients who are assigned to the control arm will be alerted when it is time to complete their T2 and T3 via app notification.
- d) For those participants assigned to Arm 1 or 2, they will complete a weekly check-in to ascertain overall safety of the patient and usefulness of coping skills practice.
- e) AE/SAE assessment and survival status will be completed via EMR review and/or telephone interview.
- f) Study completion for patients enrolled in the study is considered to occur at the completion of T3. However, participants may undergo EOS if they are withdrawn from the study by the PI or opt to withdraw from the study voluntarily at any time. Should withdraw of a patient occur, the reason for withdraw and date of withdraw will be documented. AE/SAEs and survival status will be noted, as applicable.

\*For aim 1 only.

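### The suicidal-ideation alert promised at T2 and T3 is undefined, and no item on the printed T2 or T3 form asks directly about suicidal thoughts

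*Protocol*

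**What the plan says.** Under Study Visits (protocol section 7), a patient whose T2 or T3 survey scores indicate high distress, "as defined by a triggered SI alert or increased distress score from T1", is contacted by a delegated team member. Participation ends at T3, "assuming no additional follow-up is required due to high levels of distress".

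Section 12 adds to this:

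- The oversight plan for severe distress sees a potential for "identifying underlying mental health issues through the mCST sessions, telephone calls, and survey responses", and passive suicidal ideation is among the issues it then addresses.
- Reporting Procedures promises a call when total symptom burden is high, with no threshold given. It continues: "For specific symptoms such as the suicidal ideation, a delegated study team member will also call the participant". It also says that "the study team will maintain frequent telephone contact with most participants".
- The Suicidality Response Plan has staff administer the C-SSRS to a participant judged to be at "high risk based on direct interaction plus the C-SSRS item response".
- For adverse events at each visit, "the study team will inquire by way of verbal or written request and/or EMR review". A note to Appendix 1 is similar: "AE/SAE assessment and survival status will be completed via EMR review and/or telephone interview".

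Any suicidal ideation is an adverse event for this trial (Abbreviations and Definitions). Adverse-event reports are one of the DSMB's two primary safety measures, with HADS scores the other (section 14).

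**The concern.** An alert for suicidal ideation that is read from survey scores needs a survey item that can reveal ideation, and a rule saying which answer fires it. The readable text gives no rule, and the printed T2 and T3 forms show no such item. The step that should follow, the C-SSRS, is worded as depending on its own result.

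Two things are at stake. A patient who develops ideation after enrolment could finish T3 without having been asked. And a low count of ideation events could not be taken by the DSMB as reassurance if nothing in the plan requires the question. Eligibility criterion 5b screens out active suicidality only at admission or consent, so later ideation is what the alert is there to find.

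**Working it through.** The plan states no figure to reproduce, so the check is a count of items followed by a comparison of the routes to detection.

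**Count of response items** (Appendix 3, T2 and T3 Surveys; screens numbered without a gap)

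- T2: 113 screens, less 11 information or score screens (16, 19, 34, 43, 55, 66, 80, 96, 102, 112, 113) = 102 response items.
- T3: 103 screens, less 10 (16, 19, 34, 43, 55, 66, 80, 96, 102, 103) = 93 response items.
- Cross-check by block, T2: treatment 13 + readmission 2 + social and financial 2 + HADS 14 + anxiety block 7 + PTSS 10 + physical symptoms 8 + distress ratings 3 + quality of life 1 + ADL/IADL 13 + coping 15 + mindfulness 5 + satisfaction 8 + free text 1 = 102. T3 lacks the last two blocks: 102 − 9 = 93.
- Items asking about suicide, self-harm or wishing to be dead: 0 of 102 and 0 of 93.

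The PHQ-10 does not supply one. The Abbreviations define it as physical symptoms, and its printed items are pain, weakness, breathlessness and the like. The nearest items are three on pessimism in the coping block (screens 90 to 92 on both forms), and no text ties an alert to them. The T2 free-text item asks only how the program helped.

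**Does any other route require that the patient be asked?**

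- Increased score from T1: no. It responds to change in distress.
- Call for high total burden: no. It responds to level of distress, at an unstated threshold.
- Disclosure to staff: no. The patient must volunteer it.
- Adverse-event enquiry: no. Both statements of it join record review by and/or, so record review alone satisfies them.
- Telephone contact: no. It covers most participants, and its content is not set.
- Weekly check-ins in month 1: no. They may be done by staff or in the app, and the printed forms carry no ideation item.

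**Where the gap lies.** Randomization requires HADS of at least 8 at T1. Let H be the unstated level that prompts the high-burden call. Judged on HADS alone, a patient is missed by both score-based routes when the follow-up score is no higher than at T1 and below H.

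- If H = 8 (section 5 describes HADS of 8 or more as high distress): a follow-up score of 7 or less, which is below any eligible T1 score. Example: 8 at T1, 7 at T3, change −1.
- If H = 14 (the SAP's stratification cut, used only as an illustration): any score of 13 or less that has not risen. Example: 13 at T1, 13 at T3, change 0.

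The protocol does not say that the distress score is HADS alone, so a rise in PTSS might also trigger contact and narrow the gap.

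**C-SSRS wording.** Administration follows a judgment of high risk that already uses a C-SSRS item response. The printed C-SSRS (Appendix 4) asks questions 1 and 2 first and branches from them, so a short lead-in may be meant. No survey and no row of Appendix 1 carries those questions or says when they are put.

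**The case against.** The strongest reply is that an undefined alert is not an alert without an input. It could be set on items the forms do contain, such as the pessimism items or the HADS depression items. That stands: a reader might infer that the alert can never fire, and the documents do not show this. They show only that nothing defines it and that no item asks about ideation directly.

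A reader might also infer that a severely distressed patient with a flat score, say HADS 20 at T1 and at T3, leaves the study unnoticed. The documents do not support that either. Such a patient would plausibly draw the high-burden call, since 20 is well above the only level the protocol calls high, and T3 closes participation only if distress needs no follow-up.

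Nor can one conclude that the trial has no means of detecting ideation. Besides the routes listed, all participants receive a resource list and 24-hour PI contact details. Non-serious events are recorded until 7 days, and serious events until 30 days, after the last day of participation.

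The printed forms are also imperfect evidence of the deployed app. The CSQ-8 is assigned to T3 (sections 3 and 4), but satisfaction items are printed on T2 and absent from T3. Appendix 2 and Appendix 3 A to E appear only as headings in the text available, and the DSMB charter is not supplied. Any of these might define the alert.

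Finally, the Suicidality Response Plan reports that in studies with over 400 participants, under 5% needed a PI call and none of those needed acute psychiatric referral. This tempers the severity, although how those participants were identified is not stated.

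What remains is that no readable text requires a direct question at either visit where an ideation alert is promised.

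**Conclusion.** The concern holds in a limited form and should be fixed. On the printed forms the T2 and T3 alert cannot detect ideation directly (0 of 102 and 0 of 93 items), the alert is undefined, and the C-SSRS trigger is circular as written. The exposure is confined to ideation in patients whose scores have neither risen from T1 nor reached the unstated high-burden level, and who are not picked up through disclosure, staff contact or records. No feasibility, acceptability or efficacy outcome is touched.

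Confidence is medium. The conclusion assumes that the printed T2 and T3 forms match the app and that the unavailable workflow and charter do not define the alert. If the app already carries a direct item, the point reduces to a missing definition and a sentence to reword.

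**What to change.** 1. Confirm in the deployed app, or add, one direct ideation item at T2 and T3 in all arms. Alternatively, require a direct question in the existing T2 and T3 adverse-event enquiry, so that record review alone no longer suffices. This can also serve as the interim step while the app is changed.
2. State which response fires the alert and which study role reviews it.
3. Reword the Suicidality Response Plan as a sequence: positive item or disclosure, then staff call, then full C-SSRS.

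**Cost.** A short amendment and, if the item is new, a form change. One item adds 1/102 = 0.98% at T2 and 1/93 = 1.08% at T3. That is at most 2 × 60 = 120 answers for the protocol's 60 patients, or 2 × 45 = 90 for the 45 the SAP targets.

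The real burden is prompt review, because patients answer at home. Existing staff must be assigned to it, and the screen shown after a positive answer should give the 24-hour contacts the protocol already lists. The calls themselves are already promised. At the protocol's under-5% rate they would number fewer than 0.05 × 60 = 3, or 0.05 × 45 = 2.25. At an assumed 10%, which has no source in the documents, they would be 6 of 60 or 4.5 of 45.
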